3.5.2. Storing our data safely

Once we have collected the data, all the data should be stored safely.

The participant folders should be kept locked away in the filing cabinet, even if you are still busy at the clinic/healthcare facility. You should only have the folders out that you are busy with, and you should never go and have tea, or walk away, leaving any folders, supplies or valuables outside the cabinet. This also applies to any other forms or papers related to MaRISA. If you are not busy on the tablet, please also keep it in the locked cabinet and leave the tablet in the filing cabinet at the end of your shift.

Remember: Any hardcopy forms with patient names or contact details will be stored in the CONTACT folder. All other hardcopy forms will go into the EVERYDAY folder. Each of these files will be kept in separate drawers in the stainless-steel cabinets.

CHAPTER 5: STUDY PROCEDURES

4. Introduction and Expectations

Staff should keep in mind that they are patients' first contact with the project. In doing so, the team gives patients their first impression of the project.

How you approach people, your body language, dress code, attitude and what you say will leave a lasting impression on people who are screened for the study and others. These impressions can influence whether people will want to participate or not in the study. Be conscious of the impressions you make and be careful of what you say – try and make people feel comfortable and welcome.

For the pilot testing phase, we aim to recruit 60 (30 pregnant and 30 post-partum) women for the two healthcare facilities. Both the pregnant and post-partum women need to report that they are using alcohol. Fieldworkers will conduct the baseline assessment, 6-week follow-up assessment, and the 3month follow-up assessment.

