5.2. Screening

Once introductions are made and a patient's cooperation has been secured, complete the participant ID, staff ID, site and date fields on the screener, using the tablet.

- For the pilot phase, we will be using the "Pilot Screener for Pregnant and Post-Partum Women" at the onset of the pilot phase.

Recruitment will be done via clinic referrals, posters, and flyers.

Participant IDs will be according to the following format, it will consist of ten digits with both alphabetic and numerical items, e.g., M_BL0001PR or M_BL0001PP.

Please note: the first alphabetic digit refers to the MaRISA study, an underscore sign separates it from the next 2 alphabetic digits which indicates the site, e.g., Bishop Lavis = M_BL, the next 4 digits indicates how many participants have been enrolled into the study and the last 2 digits indicates whether the participant is currently pregnant or post-partum.

There are types of potentially sensitive information that are requested on the screening questionnaire. It is important to stress the confidential nature of the screener. Reassure them that their identity will never be linked to their responses and that their responses are only used for research purposes. Always remind individuals that their answers will be kept strictly confidential.

Staff ID#: Will be a staff member's Initials.

Site ID#: Bishop Lavis = M_BL; Macassar = 002

To be eligible, women must fulfil in the following criteria, i.e.:

Criterion	Participants
Age	Be ≥ 18
Pregnancy or Post-Partum Status	be pregnant (≤ 28 ges wks) or postpartum (≤ 3 mos)
Alcohol Use	
 have reported alcohol use during the current pregnancy or lactation test positive for alcohol use by urinalysis (i.e., EtG)
Birth Venue (linked to birth outcomes)	plan to complete antenatal care at the current clinic and remain in the area for at least 3 months
Cellphone Status	own a cell phone to receive text messages
Serious Medical Conditions and Suicidal Thoughts	women who report serious medical problems threatening their current pregnancy or report current suicidal thoughts or attempts in the past month are NOT eligible
Other	intend to breastfeed for 6 months

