5.3. Baseline Assessment

Remind the participant of their rights to confidentiality and privacy in answering the questions with the exception if they indicate desire to harm themselves or someone else. Refer to the Distressed Participant Procedures (see **Chapter 6**) if a patient ever indicates they will do harm to themselves or someone else. If the participant has any questions or concerns about being in the study, they can contact the Site PI. Her contact information is on the **Information and Consent Form**.

Baseline assessment questions will be conducted via CASI on a tablet. Assessment questions will cover sociodemographic factors; social determinants; recent and lifetime polysubstance and alcohol use; IPV/GBV exposure; partner drinking; stigma; coping with stress; and reproductive, sexual, physical, and mental health.

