Maternal Alcohol Reduction Intervention in South Africa [MaRISA]

NCT05319977; May 18, 2021

Descriptive statistics will be used to describe the data for the overall sample and separately for participants enrolled while pregnant and postpartum. Data will be summarized using the mean (standard deviations) for continuous variables and percentages (frequency) for categorical variables. Changes from baseline to follow-up assessments on variables related to alcohol use and contextual/co-occurring issues (i.e., violence and depression) will be evaluated using the Cochran-Armitage Trend test. All analyses will be performed using SAS version 9.4.

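### The SAP's only test of change, Cochran-Armitage, cannot take a score or count uncut across three visits, and it treats repeated measures on the same women as independent

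*SAP*

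**What the plan says.** The SAP is a single paragraph. It plans descriptive summaries overall and separately for women enrolled pregnant and postpartum, and it covers both continuous and categorical data: "Data will be summarized using the mean (standard deviations) for continuous variables and percentages (frequency) for categorical variables". Its one inferential sentence concerns "Changes from baseline to follow-up assessments on variables related to alcohol use and contextual/co-occurring issues", and for these the method is as follows: "i.e., violence and depression) will be evaluated using the Cochran-Armitage Trend test". It gives no other test, no cut-point, no rule for turning a score into categories, and no estimate or confidence interval for change.

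The protocol (Chapter 5, Introduction and Expectations) sets the visits: "Fieldworkers will conduct the baseline assessment, 6-week follow-up assessment, and the 3month follow-up assessment". On size it says "we aim to recruit 60 (30 pregnant and 30 post-partum) women for the two healthcare facilities". Protocol 5.3 lists the assessment content by topic only, for example "recent and lifetime polysubstance and alcohol use", and names no scale, drink count or threshold. Protocol 5.2 makes a positive urine result an entry condition: "test positive for alcohol use by urinalysis (i.e., EtG").

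**The concern.** Cochran-Armitage is a test for a 2 x k table: one margin binary, the other ordered, and every observation independent. The plan strains both requirements.

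- **Scale.** With three visits as the ordered margin, the outcome must be the binary margin. The SAP expects continuous variables somewhere in the data but does not say whether any change outcome is one. If one is, the analyst must either leave it untested or choose a cut-point that the plan does not fix, possibly after seeing the data.
- **Dependence.** Each woman contributes up to three observations. The test's variance ignores this, so its p-value is wrong whatever the scale of the outcome.

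A trend p-value also does not say how much drinking, violence or depression changed, which is the quantity a 60-woman pilot most needs to pass on.

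**Working it through.** The documents give no alpha, power, SD, effect size or sample-size calculation, so there is no figure of the plan's own to reproduce. From the documents come 60 women, three visits and one test. Assumed here are a nominal two-sided 0.05, complete visits, and the correlations and distributions stated below.

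**1. Size when pairing is ignored.** For a binary outcome with prevalence p and common within-woman correlation r, the true variance of the trend statistic is (1 - r) times the variance the test uses. The test's standard error is therefore too large by a factor 1/sqrt(1 - r), and its true size is 2 x Phi(-1.96/sqrt(1 - r)).

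| r (binary) | 1/sqrt(1 - r) | true size |
|---|---|---|
| 0 | 1.00 | 0.050 |
| 0.2 | 1.12 | 0.028 |
| 0.3 | 1.20 | 0.019 |
| 0.5 | 1.41 | 0.006 |

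A simulation with three visits, 60 women, a median cut and 20,000 runs gave 0.054, 0.017 and 0.007 at latent correlations of 0, 0.5 and 0.7. This agrees with the formula. Latent 0.5 and 0.7 correspond to binary correlations of 0.333 and 0.494, for which it gives 2 x Phi(-2.40) = 0.016 and 2 x Phi(-2.76) = 0.006.

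**2. Information lost by a cut, unpaired.** For a normal score cut so that a proportion p lies on one side, efficiency relative to the mean is phi(z_p)^2 / [p(1 - p)].

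- p = 0.5: 0.15915/0.25 = 0.637, loss 36.3%, effective n = 60 x 0.637 = 38.2
- p = 0.2: 0.07838/0.16 = 0.490, loss 51.0%, effective n = 60 x 0.490 = 29.4
- p = 0.1: 0.03080/0.09 = 0.342, loss 65.8%, effective n = 60 x 0.342 = 20.5

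**3. Information lost by a cut, paired change.** Multiply the efficiency by (1 - rho)/(1 - f), where rho is the correlation of the score between visits and f that of the cut variable. At an assumed rho = 0.5:

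- p = 0.5: f = 0.333, 0.637 x 0.5/0.667 = 0.477, loss 52.3%
- p = 0.2: f = 0.295, 0.490 x 0.5/0.705 = 0.347, loss 65.3%
- p = 0.1: f = 0.249, 0.342 x 0.5/0.751 = 0.228, loss 77.2%

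From a median cut to a 10/90 cut, the loss runs 45-73% at rho = 0.3 and 62-83% at rho = 0.7.

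**4. Counts.** Under assumed negative-binomial models (means 2 to 10, dispersion 0.5 to 2, cuts at 1, 3, 5 or 10), the loss in information on the log mean ranged from 34% to 91%. The normal-score range should therefore not be applied to drink counts.

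**5. Two visits only.** Baseline against one follow-up can put time on the binary margin and an uncut score on the ordered one. With an 11-level score and 60 women, simulated size was 0.048 if the two visits were independent, but 0.008 at rho = 0.5.

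**The case against.** The strongest reply is that the scale problem is inferred. Neither document names a depression score or a drink count. The mean-and-SD sentence covers all study data and could be there for age, gestational weeks or infant measurements. The alcohol measures whose form is documented, the EtG result and reported use, are yes/no, and a test for binary outcomes suits binary outcomes. This stands in part: a reader might infer that scored outcomes are certainly left without a test, and the documents do not establish that. They do leave every outcome's scale and cut-point undefined.

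A second reply is that the SAP speaks of changes from baseline to follow-up, which could mean two-visit comparisons, and an uncut score can enter those. That also stands, so it would be wrong to say the test can never be run on a score. It does not rescue the plan, because that version still ignores the pairing (step 5).

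A third is that the planned means and percentages allow change to be worked out by subtraction. They do, but without a paired standard error or interval.

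Finally, this is a pilot with no stated hypothesis or power. That lowers the stakes of the p-value and makes a usable estimate with an interval more important.

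**Conclusion.** The point holds. The part that needs no assumption about instruments is the dependence: the same women are measured up to three times, and the test named assumes independence. Under positive within-woman correlation it is conservative, with true size of about 0.006 to 0.028 for binary correlations of 0.5 down to 0.2, and so it is prone to miss real change. A reader might expect inflated false positives; with positive correlation the error runs the other way.

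The scale problem is conditional. It applies to any outcome kept as a score or count when the three visits form the ordered factor. The 36-66% loss holds only for a normal, unpaired score cut between the median and the 10th or 90th percentile, and 52-77% is the paired counterpart at an assumed correlation of 0.5. Neither is a property of this trial's data. A reader might also infer that dichotomising would make the test valid. It would not, because the cut variable is still measured repeatedly on the same women.

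**What to change.** Replace the Cochran-Armitage sentence with a short table that lists each change outcome, its scale, any cut-point (fixed before analysis) and its method:

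- **Scores:** a linear mixed model with visit as a three-level factor, or paired change from baseline.
- **Counts (drinks, drinking days):** a negative-binomial GEE or mixed model.
- **Binary items:** a logistic GEE, or McNemar (each follow-up against baseline) or Cochran Q (all three visits). Since the last two give only p-values, add an interval for the paired difference in proportions.
- **All of these:** report change from baseline at 6 weeks and at 3 months with 95% confidence intervals.
- **EtG:** do not model change from baseline. Eligibility makes it 100% positive at entry, so a logistic model with baseline as a visit level has no finite baseline log-odds and no finite change estimate. Report the proportion positive at each follow-up with an exact confidence interval.

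The cost is SAP wording and a little more SAS 9.4 code (MIXED, GENMOD or GLIMMIX). No new data are needed.

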5.4. Follow-up Appointments and reimbursements

The participant will be reimbursed for their transport costs based on the following scale. Transport costs should only be reimbursed if the participant has needed to travel to come to the healthcare facility for a study appointment:

Categories of distances	Amount provided
0km – 3km	R10
4km – 10km	R30
11km +	R50

Pilot Phase:

In addition to monitoring participants' through urinalysis twice a week, participants will be asked to participate in the 6-week and 3-month follow-up assessments at the healthcare facility they were enrolled at.

A participant will be provided R150.00 each at baseline and follow-up assessments.

Consent will be obtained to collect participants' birthing facility information for those who were recruited during pregnancy to track birth outcomes. If a participant is already postpartum and breastfeeding, self-reported incidents of breastfeeding while using alcohol will be collected. Infants' data relating to their height, weight, and head circumference will be collected.

If a participant misses a visit, we will contact the participant following a standard protocol (i.e., phone call on the appointment day, the following day, and 1 week after the missed visit to encourage rescheduling for the missed appointment). Participant locator information will also be updated at each appointment. Staff members need to

prioritize tracking participants who have the least number of days left before their upcoming appointment so that they do not time out of the study. In other words, you should contact participants first whose next appointment is closest to the current date.

If a participant has withdrawn from the study or has reported the loss of her foetus/baby to field staff and this was reported to Project Coordinator, the participant should not be tracked any longer. These participants will also not be replaced in the study since they have been reported on.

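### The SAP's only test of change is a trend test with no scores or contrasts stated; run once over the three visits, it is nearly blind to a 6-week change that is largely reversed by 3 months

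*SAP*

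**What the plan says.** The SAP is a single paragraph. After descriptive summaries, its one inferential sentence takes "Changes from baseline to follow-up assessments on variables related to alcohol use and contextual/co-occurring issues" (violence and depression are the examples given) and says that they "will be evaluated using the Cochran-Armitage Trend test". It adds that "All analyses will be performed using SAS version 9.4". It gives no visit scores, no procedure, no alpha and no main time point. It does not say whether the visits enter one test or several, and it names no estimate of change.

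The protocol (Chapter 5, Introduction and Expectations) fixes the visits: "Fieldworkers will conduct the baseline assessment, 6-week follow-up assessment, and the 3month follow-up assessment". The same section gives the size: "we aim to recruit 60 (30 pregnant and 30 post-partum) women for the two healthcare facilities". On women who withdraw or lose the pregnancy or baby, Section 5.4 says: "These participants will also not be replaced in the study since they have been reported on". Numbers can therefore differ between visits.

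**The concern.** The SAP's question is change from baseline at each follow-up. A linear trend test answers a narrower one: whether the proportion rises or falls steadily across ordered visits. With three visits the middle one sits near the centre of the scores and contributes little.

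An early fall in drinking that fades is a plausible course in an alcohol pilot. Under a single three-visit test, such a fall could be reported as no evidence of change. A later trial would also lack a within-woman effect size and interval to plan from. Adjusting for repeated measures would not cure this by itself, because a repeated-measures model with a linear visit score has the same blind spot.

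**Working it through.** **Inputs.** Three visits and 60 women: protocol, Chapter 5. Test: SAP. The documents give no alpha, power, effect size or p-value, so there is no figure of the plan's own to reproduce. The rates, scores and losses below are assumptions for illustration; p-values are two-sided. The trend test treats visits as independent groups, so its p-values here show what the planned test would print, not valid inference for repeated measures.

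**Formula.** For visit i with count x_i of n_i and score s_i, let s̄ = Σn_i s_i / N and p = Σx_i / N. Then T = Σx_i(s_i − s̄), V = p(1−p) Σn_i(s_i − s̄)², and z = T/√V. The weight of a visit is s_i − s̄.

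**Weights, equal n.**
- Scores 0, 1, 2: s̄ = 1, weights −1, 0, +1, so T = x₃ − x₁.
- Scores 0, 6, 13 (weeks): s̄ = 6.33, weights −6.33, −0.33, +6.67. The 6-week weight is about 5% of either end.

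**Results, 60 women per visit.**

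| Assumed course | Counts | Scores | T | V | z | p |
|---|---|---|---|---|---|---|
| 90/50/90% (all of the fall lost) | 54/30/54 | 0,1,2 | 0 | 21.47 | 0.00 | 1.00 |
| same | 54/30/54 | 0,6,13 | 8 | 908.8 | 0.27 | 0.79 |
| 90/50/80% (three-quarters lost) | 54/30/48 | 0,1,2 | −6 | 23.47 | −1.24 | 0.22 |
| 90/50/70% (half lost) | 54/30/42 | 0,1,2 | −12 | 25.2 | −2.39 | 0.017 |

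In the last row T = 42 − 54. The 6-week count enters only through V.

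**Unequal n.** With 80/40/80%, scores 0, 1, 2 and n = 60/50/40, s̄ = 130/150 = 0.867, so the 6-week weight is 1 − 0.867 = +0.13; T = −2.67, V = 21.63, p = 0.57. With n = 60/45/30 the weight is +0.22 and p = 0.35. The weight is no longer zero, but the fall is still missed.

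**Dependence on scores.** Scores 0, 1, 1 (baseline against any follow-up) give weights −0.67, +0.33, +0.33. For 54/30/54, T = −36 + 28 = −8, V = 7.16, z = −2.99, p = 0.003. The same data thus give p = 1.00 or p = 0.003 depending on a choice that the SAP leaves open.

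**Separate two-visit reading.** Baseline against 6 weeks, 54 and 30 of 60, scores 0, 1: p = 84/120 = 0.70, T = −12, V = 0.21 × 120 × 0.25 = 6.3, z = −4.78, p < 0.0001. This is the unpaired 2x2 chi-square without continuity correction. It detects the fall but treats 60 women seen twice as 120 independent women.

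**What a paired contrast gives for the same fall.** Let b women stop and c start. The difference is (b − c)/n, with SE = √[(b + c) − (b − c)²/n]/n.
- b = 24, c = 0: 40 points, SE = √(24 − 9.6)/60 = 0.063, 95% CI 27.6 to 52.4; exact McNemar p = 1.2 × 10⁻⁷.
- b = 27, c = 3: 40 points, SE = √(30 − 9.6)/60 = 0.075, 95% CI 25.2 to 54.8; exact McNemar p = 8.4 × 10⁻⁶.

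**Power.** Simulated trials used n = 60, an assumed within-woman latent correlation of 0.4, scores 0, 1, 2 and a two-sided 5% level. At 90/50/80% the three-visit trend test rejects in about 15% and the paired baseline-to-6-week test in about 100%. At 80/50/75% the figures are about 4 to 5% and 97%.

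**The case against.** The strongest reply is that the SAP does not say that the three visits enter one test. Its plural, follow-up assessments, fits two separate tests equally well, and the baseline-to-6-week test would then find the fall. That stands. A reader might infer that the SAP never tests change at 6 weeks; the text does not support this. What remains on that reading is an unpaired test of paired data and an unstated contrast.

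Three other strong readings also fail:
- **The 6-week weight is always zero.** It is exactly zero only under particular combinations of scores and numbers, such as equal spacing with equal n. The SAP gives no scores, and unreplaced losses make equal n unlikely.
- **A rebound gives p = 1.** That also needs an exact return to the baseline rate. For the urine marker, where entry requires that women "test positive for alcohol use by urinalysis (i.e., EtG", full return would mean that every woman is positive at 3 months.
- **Any partly lost fall is missed.** The 90/50/70% row shows otherwise.

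The planned percentages and means, if tabulated by visit, would show a 6-week fall and its raw size. The twice-weekly urine monitoring (protocol, Section 5.4) also bears on the short-term course. This is a partial answer: the SAP promises neither by-visit tables nor intervals, and names no analysis of the monitoring data.

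Finally, if 3 months is what matters most, the equally spaced three-visit test already targets that difference. True, but the documents name neither follow-up as main.

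**Conclusion.** The concern holds in a conditional form. The SAP leaves scores and contrasts open. If the test is run once over three visits with visit-order or week scores, it has almost no sensitivity to a 6-week change that is largely or fully reversed: p = 0.22 to 1.00 in the 90% examples with 60 per visit, and 0.35 to 0.57 in the two examples with losses. With equal spacing and equal n the numerator reflects only the baseline-to-3-month difference, so even a significant result says nothing about 6 weeks. If two separate tests were meant, the fall is detectable but the pairing is ignored. Neither reading commits the sponsor to a within-woman estimate with an interval.

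The zero weight is exact algebra under its stated conditions. The sizes rest on assumed rates, losses, scores and correlation. In a 60-woman pilot with no stated power or alpha, this is a should-fix.

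**What to change.** Replace the trend test with two prespecified contrasts per outcome: baseline to 6 weeks and baseline to 3 months. Report each as a within-woman difference with a 95% CI, for example from a repeated-measures model with visit as a three-level factor and not a linear score. For a yes/no outcome this is a difference in proportions; for a continuous one, a difference in means. If every woman is EtG-positive at baseline by entry, a logistic model cannot estimate that baseline level, so report the EtG change directly as a paired difference in proportions.

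State in advance which contrast is main. The documents do not settle this, so the choice is the sponsor's.

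The cost is a few sentences in the SAP and a few lines of SAS. Visits, sample size and data collection stay as they are. The downside is two contrasts per variable instead of one test, which naming a main contrast keeps in hand.

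### The SAP assesses change only with a trend test that ignores repeated measurement, and plans no within-woman change from baseline with a confidence interval

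*SAP*

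**What the plan says.** The SAP is a single paragraph with two analytic parts.

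- **Description.** "Data will be summarized using the mean (standard deviations) for continuous variables and percentages (frequency) for categorical variables". This is done "for the overall sample and separately for participants enrolled while pregnant and postpartum". The SAP does not say that these summaries are given visit by visit, or that change itself is summarised.
- **Change.** Changes from baseline to the follow-up assessments in alcohol-related variables, violence and depression "will be evaluated using the Cochran-Armitage Trend test". No mean change, difference in proportions, odds ratio or confidence interval is named. No significance level is stated.

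The protocol (Chapter 5, Introduction and Expectations) sets the size and schedule: "we aim to recruit 60 (30 pregnant and 30 post-partum) women for the two healthcare facilities", and "Fieldworkers will conduct the baseline assessment, 6-week follow-up assessment, and the 3month follow-up assessment". Section 5.4 says that women who withdraw, or who report losing the pregnancy or baby, are no longer tracked and are not replaced. Section 5.2 requires both reported alcohol use in the current pregnancy or lactation and a positive EtG urine test; its disposition table lists failing either one as a ground for not enrolling. The protocol contains no further analysis plan and no power or precision basis for 60.

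**The concern.** A trend test says whether an ordered difference between visits is larger than chance would produce. It does not say how large the change is or how well it is known. A pilot of 60 women should chiefly deliver those two things, because the next study will be planned on them. Without them, a non-significant result can be read as no change when the data are compatible with a substantial fall. A significant result carries no stated size.

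The test also assumes that the three visits are independent samples. Here each woman contributes to all three, so the precision of the change depends on how many women moved in each direction. Visit percentages do not contain that information, and the SAP reports it nowhere.

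**Working it through.** There is no planned precision or power figure to reproduce. The documents give the numbers of women and the visits. All rates, correlations and counts below are assumptions, with two-sided 5% and no dropout.

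**1. Same percentages, same p, different intervals.** Take a yes/no measure not fixed by eligibility, such as a positive depression screen, with assumed counts 21, 18 and 15 of 30 (70%, 60%, 50%).

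- Cochran-Armitage with scores −1, 0, 1: Z = (x₃ − x₁)/√[p̄(1 − p̄)·2n]. Here p̄ = 54/90 = 0.6, so Z = −6/√(0.24 × 60) = −6/3.795 = −1.58, p = 0.114.
- Change to 3 months: −6/30 = −20 points.
- Let b women go from positive to negative and c the other way, with d = (b − c)/n the fall. The large-sample SE is √{[(b + c)/n − d²]/n}.
- The score interval is the set of d with |b − c − nd|/√{n[2q + d(1 − d)]} ≤ 1.96, where q = [√(B² − 4AC) − B]/(2A), A = 2n, B = −b − c + (2n − b + c)d and C = −c·d(1 − d).

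| b, c (n = 30) | Half-width, large-sample | 95% score interval for the change |
|---|---|---|
| 9, 3 | 1.96 × √(0.36/30) = 21.5 points | −41.2 to +2.9 |
| 7, 1 | 1.96 × √(0.2267/30) = 17.0 points | −38.6 to −1.9 |

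Both rows have the same visit percentages and the same trend p. I put no weight on the second interval stopping just short of zero, since the exact McNemar p is 0.070. What matters is that the width depends on b and c.

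With every count doubled (n = 60), Z = −12/√(0.24 × 120) = −2.24, p = 0.025. The score intervals are −35.1 to −4.2 (18, 6) and −32.9 to −7.9 (14, 2). The test is now significant, but p does not show that the fall could be about 4 points or 35.

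**2. How often a real fall would be missed.** Three visits were simulated 20,000 times per setting, with a true 20-point fall (60-50-40%, 70-60-50% or 80-70-60%) and latent within-woman correlation of 0, 0.5 or 0.7.

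| | n = 30 | n = 60 |
|---|---|---|
| Trend test power | 29–40% | 61–73% |
| Median half-width, paired 95% CI for baseline to 3 months | 17–25 points | 12–18 points |

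A real fall of this size is missed in 60–71% of runs at 30 and 27–39% at 60. For a mean change, the half-width is t/√n: 0.37 SD of the change at n = 30 and 0.26 SD at n = 60.

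**3. Effect of ignoring the pairing.** With no true change (60% at every visit), the simulated type I error of the trend test is about 5% at correlation 0, 1.6–1.7% at 0.5 and 0.6% at 0.7. The test is therefore conservative. At n = 60 and correlation 0.5–0.7, it detects the 20-point fall in 63–73% of runs. The large-sample paired interval excludes zero in 77–92%, with type I error near 5%. I make no such comparison at n = 30, where that interval is liberal (about 7%).

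**4. A measure at 100% on entry.** For EtG, assume 30, 27 and 25 of 30. Then p̄ = 82/90 = 0.911 and Z = −5/√(0.911 × 0.089 × 60) = −2.27, p = 0.023. No woman can change from negative to positive, so the change is simply the 5/30 = 16.7% negative at 3 months. The exact (Clopper-Pearson) 95% interval is 5.6% to 34.7%, obtainable from that visit's count alone. For 100-90-80% with independent visits, simulated power is about 80% at n = 30 and 99% at n = 60.

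**The case against.** The strongest reply is that the entry rule fixes the main alcohol measure at about 100%. There the trend test has fair power, and a reader can rebuild the interval from the follow-up percentage and the number tested. This stands (step 4), so it would be wrong to infer that readers can never recover the interval. The point applies to measures not at that ceiling: violence, depression, and items on recent or heavier drinking. The SAP does not list its alcohol variables, so some may be of this kind.

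Second, a crude change is available by subtraction if the summaries are tabulated by visit. This also stands, although the SAP does not promise that layout. What would still be missing is the paired interval.

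Third, a reader might infer that the plan decides by a p threshold, ranks the p-value as its main output, or runs the test in groups of 30. The SAP says none of these. It states no significance level or decision rule, it opens with description, and it gives the enrolment split for the descriptive summaries only. That is why the working covers both 30 and 60.

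Fourth, the low power comes partly from using a test for independent samples, which is a different fault from omitting an interval. That is fair, but the same paired estimate cures both.

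**Conclusion.** The point holds in bounded form. Followed exactly, the SAP yields a Z and p for change and no estimate of within-woman change with its uncertainty. For measures not fixed at 100% by eligibility, a non-significant result cannot be told apart from low precision, whether the test uses 60 women or 30. Under an assumed 20-point fall from a 60–80% start, non-significance is the likelier outcome at 30 and occurs in roughly a quarter to two-fifths of trials at 60. Unreplaced withdrawals can only reduce those numbers.

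The sizes rest on assumed rates and correlations. That no change estimate or interval is planned, and that the test does not use the pairing, does not depend on them. The study remains valid and the data needed are already being collected, so this should be corrected but does not undermine the design.

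**What to change.** In the SAP, make the main result for each alcohol, violence and depression variable the within-woman change from baseline to 6 weeks and from baseline to 3 months, with its 95% CI and the number of women contributing, overall and by enrolment group. Any p-value should be secondary.

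- **Yes/no measures:** a small-sample paired interval, for example a score-based interval for a paired difference in proportions. Tabulate the numbers changing in each direction.
- **Measures at 100% by entry criterion:** an exact interval for the follow-up proportion.
- **Means:** a paired t interval for the change.
- **Missing visits:** state that each estimate covers women assessed at both visits, and report how many are missing at each time point and in each group.
- **EtG:** note that because a positive test is required for entry, a later fall partly reflects selection.

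The cost is SAP wording and more output: two time points by three populations gives six estimates per variable. Many intervals will be wide and will look less favourable than a lone p-value. No new data, visits or participants are needed.
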